Recruitment Procedures The enrollment of 180 depressed HIV positive, cART suppressed individuals will be accomplished through the implementation of a series of structured and well-coordinated recruitment and screening activities. These activities include: 1) the use of the Penn CFAR HIV clinical registry; 2) traditional advertising via fliers and print media; 3) networking with MH and HIV clinicians, clinic staff, case managers and patients; and 4) regular presence at clinic staff meetings to provide project visibility and feedback on project enrollment. We will post the IRB approved flyers in key locations and on the PMHARC HIV Research Bulletin Board, a web site that provides a central location for posting IRB recruitment flyers. We will begin recruitment by targeting the five adult HIV clinics that operate under the umbrella of the University of Pennsylvania Health System (UPHS). The UPHS clinics serve approximately 2,000 patients each year and are linked administratively, share a common database and electronic medical record system. We will also recruit participants from the Drexel Partnership Clinic, the Temple HIV Clinic and the Lax Clinic of Philadelphia Fight. Thus, collectively the clinics from which we will be recruiting see approximately 7,500 patients each year. Recruitment will be initiated upon notice of grant award and enrollment will begin in the fourth month of the study and continue for 53 months. **Power Analysis and Sample Size Calculation for Primary Aims** We used two-sided hypothesis tests, and assumed 10% loss to attrition over the 10 weeks. We set an overall alpha level of 5% within the innate immunity and inflammation hypotheses, so each Hypothesis is tested at $\alpha=0.025$. We used the methods of Hedeker et al. (152): assuming a within person correlation of 0.6 between visits, we have 80% power to detect a linear group by time effect (from week 0 through week 10) of Cohens $d=0.42$ or higher, and 80% power to detect a main effect (from week 2 through week 10) of $d=0.41$ or higher. **Biostatistical Consideration and Analysis Plan for Primary Aims** For Primary Aims 1A and 1B, participants will provide measures of innate immunity and inflammation at baseline, and at weeks 2, 4, and 10. The measures will be continuously distributed, and we will use linear mixed effects models, probably after log transformation of a response, to estimate the effects of medication group and time on the distribution of the responses across the 10 week period. The explanatory variables in these models will be a binary indicator of medication group, variables representing time effects, together with possible group by time interaction terms. Time will be modeled as a discrete factor. For the covariance structure, we expect that a random intercept model will provide a good fit to the data, and will also compare other possible specifications using BIC comparisons. **Biostatistical Consideration and Analysis Plan for Secondary Aim First**, we will examine whether participants showing improvement in depression measures are also those showing improvement in primary biological measures. Here, we will calculate change from baseline scores for the HAM-D and for the four immunity measures. For each immunity measure and HAM-D, we will use bivariate mixed

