BDI II for subjective ratings of depressive symptoms; 5) C-SSRS to assess suicidal ideation; 6) Medical history and vital signs; 7) Neuropsychological assessment to exclude HAD; 8) HIV plasma RNA viral load test; 9) Biological assessment: comprehensive immune, virologic and neuroendocrine measures, a complete blood count (CBC), and a comprehensive metabolic panel (CMP); and 10) Pregnancy test. These procedures may happen at our research offices, remotely via private video or telephone call, or on our Mobile Clinical Trials Unit (MCTU). The SCID-RV, HAM-D, and C-SSRS will be audio recorded for training purposes on a digital audio recorder or on Bluejeans. Subjects will also sign a release of information to allow us to communicate with their HIV primary care provider. The baseline assessment may be completed in one longer visit (8-10 hours) or two shorter visits (each 4-5 hours).

Randomization The 180 HIV-seropositive eligible and consenting depressed subjects will be randomized to 10 weeks of double blind therapy with either escitalopram or placebo. Study medication may be sent to participants via mail. All participants will concurrently begin CCBT. Stratification based on race, sex, and baseline depression symptom severity, will be incorporated to ensure an even distribution of more severely depressed subjects (i.e., those with HAM-D scores greater than or equal to 20) in each treatment condition. Neither the research nurse nor the study clinicians will be aware of the assigned treatment condition for each subject nor will any research staff having any clinical contact with the study participants be aware of the treatment assignment during each subjects participation in the study. Only the research pharmacist will be unblinded to the treatment condition during each subjects participation.

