Previously we demonstrated that major depression is associated with significant reductions in NK cell activity and resolution of depression resulted in improvement of LUNK (for details see C1.7, C1.8). SSRI enhances LUNK ex vivo (for details see C1.9.a). In addition as a part of our recent project (RO1 MH82670) we demonstrated that increase in severity of depression is associated with decrease in absolute numbers of total NK cells ($p=0.008$), reduction in perforin+ NK cells ($p=0.009$) and reduced expression of activation receptors NKP30+ ($p=0.011$) and NKP46+ ($p=0.049$) (unpublished observations). NK cell functions are also affected by HIV infection in several ways including decreased cytotoxic activity, changes in receptor expression and cytokine production (123-125). Although NK functions are partially restored by cART(44, 123), several studies demonstrated that recovery is incomplete. NK cells from HIV positive individuals with sustained viral suppression by cART do not completely recover in numbers (44), continue to have increased activation/degranulation profiles (46), show decreased receptor expression (NKP46 and NKP30) (126) and decreased cytokine production (IFNy, TNF- α) (127).

In this aim we will assess NK cell functions in HIV positive individuals on stable cART at baseline and after 2, 4, and 10 weeks of SSRI therapy. NK cell function will be assessed by the standard chromium release assay, established in our laboratory, using K562 target cells and peripheral blood mononuclear cells (PBMC) at effector to target cell ratios of 6.25 - 50. Percent lysis values will be normalized for percent NK cells within the PBMC preparations and are expressed as lytic units (LU) per 10^7 NK cells or LUNK as previously described (41, 71, 72). In addition intracellular IFNy will be assessed as described (42) (also see letter from [name]) in stimulated PBMCs. The number of IFNy+ NK cells will be assessed by flow cytometry gated on CD45+/CD3/ CD16+/CD56+ cells. Nonreactive isotype-matched mAb will be used as control.

Aim 1B. Determine whether an SSRI downregulates

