Primary Aims: For Primary Aims 1A and 1B, participants will provide measures of innate immunity (LUNK and intracellular IFN- γ) and inflammation (IL6 and CRP) at baseline, and at weeks 2, 4, and 10. The measures will be continuously distributed, and we will use linear mixed effects models, probably after log transformation of a response, to estimate the effects of medication group and time on the distribution of the responses across the 10 week period. The explanatory variables in these models will be a binary indicator of medication group, variables representing time effects, together with possible group by time interaction terms. Time will be modeled as a discrete factor. For the covariance structure, we expect that a random intercept model will provide a good fit to the data, and will also compare other possible specifications using BIC comparisons.

Secondary Aim: In the Secondary Aim, we will examine relationships between the effects of Escitalopram versus Placebo on depressive symptoms and the effects on the primary biological responses. Hamilton scores will be obtained at baseline and at weeks 2, 4, and 10.

First, we will examine whether participants showing improvement in depression measures are also those showing improvement in primary biological measures. Here, we will calculate change from baseline scores for the Hamilton and for the four immunity measures. For each immunity measure and Hamilton, we will use bivariate mixed effects models to simultaneously model the pattern of depression change scores and immunity change scores across weeks 2 through 10. Here, for each of the four immunity measures, we are modeling the three Hamilton change scores and the three immunity change scores as a six-dimensional response, with explanatory variables of week, medication, and type of response (depression versus immunity). Our hypotheses, that decreases in Hamilton will be associated with increases in innate immunity, and with decreases in inflammation, will be tested by modeling the covariance structure, and testing individual covariances for significant differences from zero. We will perform these analyses separately for the four immunity responses.

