Second, we will test whether Escitalopram has direct and indirect effects on the immune responses. The primary analyses (for Aims 1A and 1B) have addressed the total effect of Escitalopram on the four immunity measures. One set of analyses will use the confidence limit approach of MacKinnon et al (135, 136), to test whether changes in Hamilton score at week 2 (and, separately, at week 4) mediate the change in immunity measures at week 10. To obtain a complete picture of the possible mediation effects of depression, we will also perform these analyses using 50% reduction in HAM-D, and HAM-D ≤ 7 , as the measures of the direct effect of Escitalopram on depression. We will perform these analyses on the four innate immunity and inflammation responses separately. These mediation analyses focus on the end of treatment time point. To obtain information on longitudinal mediation across the full period, we will use latent growth curve mediation models (MacKinnon, 2008, 8.10-8.14). These models are similar to the bivariate mixed effects models described above, but here we include additional regression terms to isolate effects of depression on immunity across time, and random intercepts and slopes for the repeated depression scores and the repeated immunity scores, with the intercept and slope of the immunity response regressed on the intercept and slope of the depression response. MacKinnon (2008) describes how the estimated coefficients of these models can be used to provide estimates and confidence intervals for the indirect and direct effects of Escitalopram on immunity.

C.3.2.b Power Analysis and Sample Size Calculation for Primary Aims

We use two-sided hypothesis tests, and assume 10% loss to attrition over the 10 weeks. We set an overall alpha level of 5% within the innate immunity and inflammation hypotheses, so each Hypothesis is tested at alpha=0.025. We use the methods of Hedeker et al (122): assuming a within person correlation of 0.6 between visits, we have 80% power to detect a linear group by time effect (from week 0 through week 10) of Cohen's $d=0.40$ or higher, and 80% power to detect a main effect (from week 2 through week 10) of $d=0.4$ or higher.

C.3.3 Expected Outcomes, Potential Problems and Alternative Approaches

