Effects of patient characteristics: Differences in patient demographics (such as age and gender) and characteristics (such as depression severity, levels of life stress, social support, neurocognitive capacity, time since HIV diagnosis, endocrine status, and systemic inflammation level) could potentially moderate the effects of SSRI treatment on our primary outcomes. Some research has suggested that baseline levels of CRP (139), IL-6 and TNF- α (7, 86, 140, 141) and of other biological indicators (7, 86, 132) may influence the effects of

SSRI on depression. We will perform a series of moderator analyses (142) to address these questions. The potential moderators will be included as main effects and as interactions with group in the analyses described above for the primary responses. We will use multivariate analyses analogous to the univariate analyses to examine SSRI effects on a wider range of biological responses to include endocrine hormones (cortisol, ACTH, DHEA), as well as the flow cytometry panels noted above.

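### The Aim 1 models leave out the randomisation strata (race, sex, HAM-D severity), so the weeks 2–10 main-effect test is conservative to the extent that the strata predict the markers

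*Protocol*

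**What the plan says.** Under Procedures, Randomization, the protocol states: "Stratification based on race, sex, and baseline depression symptom severity, will be incorporated to ensure an even distribution". The severity stratum separates "those with HAM-D scores greater than or equal to 20" from the rest.

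The Aim 1 model is given in the protocol's Accrual section and in SAP C.3.2.a, in matching terms. The explanatory variables are "a binary indicator of medication group, variables representing time effects, together with possible group by time interaction terms". Neither text names a stratification factor or a baseline covariate, and the SAP does not mention stratified randomisation at all. A random intercept is the expected covariance structure.

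SAP C.3.2.b powers two contrasts. One is a linear group-by-time effect over weeks 0 to 10. For the other it claims "80% power to detect a main effect (from week 2 through week 10) of" d = 0.4 (0.41 in the protocol). Neither document says which contrast is primary.

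Gender and depression severity enter a model only under SAP C.4, Further Analyses: "The potential moderators will be included as main effects and as interactions with group in the analyses described above for the primary responses". Race is not named there.

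**The concern.** Balancing the arms within strata removes between-stratum variation from the true sampling variance of a between-subject group contrast. A model that ignores the strata still counts that variation as noise. Its standard error is then larger than the real variability of the estimate, the test rejects a true null less often than its nominal level, and the confidence interval is wider than it needs to be.

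What is at stake is power, and only if the strata predict the markers. The documents give partial support for one factor: SAP C.3.1 (Aim 1A) reports that "increase in severity of depression is associated with decrease in absolute numbers of total NK cells" (p = 0.008), with related findings for perforin-positive NK cells and two activation receptors (p = 0.009 to 0.049). Nothing in either document shows race or sex to be prognostic, or any of the three factors to predict IFN-γ, IL-6 or CRP.

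**Working it through.** **Inputs from the documents.** 180 subjects, half per arm; 10% attrition, so 162 analysed, 81 per arm; within-person correlation 0.6; three post-baseline visits (weeks 2, 4, 10); two-sided alpha 0.025; 80% power.

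**Assumed input.** R², the share of the variance of the weeks 2–10 subject mean explained by the strata, is not given. The range used is 0 to 15%.

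**Step 1: reproduce the plan's figure.** In single-visit SD units:
- variance of the three-visit mean = (1 + 2 × 0.6)/3 = 0.733
- SE of the group difference = √(2 × 0.733/81) = 0.1346
- detectable d = (2.2414 + 0.8416) × 0.1346 = 0.415

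The protocol states 0.41, and power at 0.41 on these inputs is 79.0%. The stated figure therefore corresponds to an unadjusted post-baseline mean.

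**Step 2: effect of leaving out the strata.** Let s = √(1 − R²). With allocation balanced within strata, the true SE is s times the SE that the unadjusted model reports.
- True size = 2 × P(Z > 2.2414/s)
- Power at d = 0.415: Φ(0.8416/s) without strata; Φ(3.083/s − 2.2414) with strata
- Detectable d: 0.1346 × (2.2414 + 0.8416s) without; 0.1346 × 3.083s with

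Worked at R² = 10%: s = 0.9487. Size = 2 × P(Z > 2.363) = 0.018. Power without strata = Φ(0.887) = 81.2%; with strata = Φ(1.008) = 84.3%.

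| R² of weeks 2–10 mean | True size without strata | Power without | Power with | Gain (points) | Detectable d without → with | Equivalent extra subjects |
|---|---|---|---|---|---|---|
| 0 | 0.025 | 80.0% | 80.0% | 0 | 0.415 → 0.415 | 0% |
| 2% | 0.024 | 80.2% | 80.9% | 0.6 | 0.414 → 0.411 | 1.5% |
| 5% | 0.0215 | 80.6% | 82.2% | 1.6 | 0.412 → 0.404 | 4% |
| 10% | 0.018 | 81.2% | 84.3% | 3.1 | 0.409 → 0.394 | 8% |
| 15% | 0.015 | 81.9% | 86.5% | 4.6 | 0.406 → 0.382 | 13% |

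Gains are taken from unrounded values. The last column is the squared ratio of the two detectable effects, minus 1.

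**Step 3: if the baseline marker were also a covariate.** The documents do not specify this. With v = 0.733 × R² as a time-constant stratum variance, effective R² = 1 − [(0.733 − v) − (0.6 − v)²/(1 − v)]/0.373. R² of 5%, 10% and 15% falls to 1.6%, 3.4% and 5.3%, and size is 0.024, 0.023 and 0.021. Putting these into the Step 2 formulas, at an effect giving 80% nominal power, leaves gains of about 0.5, 1.1 and 1.7 points.

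**Step 4: simulation.**
- Eight strata, balanced allocation, 8,000 runs per setting, R² = 15%. The SD of the estimate is the same without and with strata (0.1237 and 0.1236), so true precision is unchanged. Null rejection for the main effect is 0.016 without strata and 0.024 with; power at d = 0.415 is 82.0% and 86.3%. Null rejection for linear group-by-time is 0.024 and 0.023.
- A separate simulation used permuted blocks of 4 (assumed) in unequal strata. With strata explaining 20% of single-visit variance (0.20/0.733 = 27% of the mean), the unadjusted main-effect test rejected a true null at 0.008 under stratified allocation but at 0.026 under simple randomisation. The loss therefore comes from pairing stratified allocation with an unadjusted model.

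**The case against.** The strongest reply is about weight. The error is conservative, the estimate is unbiased, and power without the strata stays at or above 80% in every row. R² is wholly assumed, and the 10% and 15% rows have no support in the documents. The SAP's severity findings are unpublished and concern NK counts and receptors, none of which is a primary outcome. LUNK is expressed per NK cell, so a link with NK number does not carry over directly. Every subject is depressed at entry (HAM-D at least 13), and the stratum is only a split at 20. If the group effect is read from group-by-time terms, constant stratum effects cancel; if baseline is a covariate, most of the gain disappears. At R² of 2–5% the change in detectable d is no larger than the gap between the protocol's 0.41 and the SAP's 0.4. Race categories, block size and algorithm are not given, and imperfect balance would shrink the conservatism. The C.4 moderator models also already include severity and gender.

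All of this bears on size, and it keeps the point modest. It does not remove it. The weeks 2–10 main effect is one of only two powered contrasts, its stated detectable effect matches an analysis without baseline adjustment, and no baseline covariate is specified. The C.4 models are further analyses, not the Aim 1 test.

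**Conclusion.** The concern holds. The trial is randomised within strata that its primary models ignore. If the weeks 2–10 main effect is the primary contrast, the cost runs from nothing at R² = 0 to 1.6 points of power at 5% and 4.6 points at 15%, with true size falling from 0.025 to 0.0215 and 0.015. These figures rest on an assumed R², near-balanced allocation within strata, stratum effects constant over visits, and no adjustment for the baseline marker. For the linear group-by-time contrast under a random intercept there is essentially no loss unless the strata also predict change. There is no bias and no inflation of type I error, and the plan's power figures are not wrong for this reason. The change should be made as an inexpensive gain in efficiency; confidence that it matters in practice is medium because R² is unknown.

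**What to change.** In SAP C.3.2.a and the protocol's analysis plan for the primary aims, add race, sex and the HAM-D stratum (20 or more versus below), coded as used in the randomisation, as fixed effects in every Aim 1 model. Fix a rule for pooling sparse race categories before unblinding. State whether the weeks 2–10 main effect or the weeks 0–10 group-by-time effect is primary.

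The cost is one or two lines in each document and a few degrees of freedom out of about 180 subjects. The factors are already recorded at randomisation, so no new data are needed.

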Protocol Title: SSRI Effects on Depression and Immunity in HIV/AIDS

NCT Number: NCT02620150

Document: Statistical Analysis Plan

Document Date: March 10, 2015

C.3 Research Design and Methods

Aim 1 Determine the effects of an SSRI on innate immunity and inflammation in depressed HIV seropositive individuals.

C.3.1 Summary

This will be the first placebo-controlled RCT to determine the immunomodulatory effects of SSRI therapy among a contemporary, urban cohort of HIV-seropositive individuals whose viral load is well controlled, yet still experiences immune dysregulation due to co-morbid depression and HIV infection. Comparing the two depressed groups that are randomly assigned to receive SSRI or placebo will allow us to address novel aims: can SSRI treatment and improvement of depression reverse the immune dysregulation of depression and HIV. Comprehensive biomarkers of innate immunity, and inflammation will be assayed via blood draw at baseline and at 2, 4, and 10 weeks. Additionally, we will monitor adherence to SSRI and antiretroviral medications in all participants using contemporary methodology (i.e., self-reported doses taken and missed, medication electronic monitoring system (MEMS) caps, and, for HIV, plasma viral load).

Aim 1A. Determine whether an SSRI upregulates innate immunity in depressed HIV seropositive individuals.

Hypothesis: SSRI is superior to placebo in restoring biomarkers of innate immune suppression (LUNK and intracellular IFNy in NK cells).

Previously we demonstrated that major depression is associated with significant reductions in NK cell activity and resolution of depression resulted in improvement of LUNK (for details see C1.7, C1.8). SSRI enhances LUNK ex vivo (for details see C1.9.a). In addition as a part of our recent project (RO1 MH82670) we demonstrated that increase in severity of depression is associated with decrease in absolute numbers of total NK cells ($p=0.008$), reduction in perforin+ NK cells ($p=0.009$) and reduced expression of activation receptors NKP30+ ($p=0.011$) and NKP46+ ($p=0.049$) (unpublished observations). NK cell functions are also affected by HIV infection in several ways including decreased cytotoxic activity, changes in receptor expression and cytokine production (123-125). Although NK functions are partially restored by cART(44, 123), several studies demonstrated that recovery is incomplete. NK cells from HIV positive individuals with sustained viral suppression by cART do not completely recover in numbers (44), continue to have increased activation/degranulation profiles (46), show decreased receptor expression (NKP46 and NKP30) (126) and decreased cytokine production (IFNy, TNF- α) (127).

In this aim we will assess NK cell functions in HIV positive individuals on stable cART at baseline and after 2, 4, and 10 weeks of SSRI therapy. NK cell function will be assessed by the standard chromium release assay, established in our laboratory, using K562 target cells and peripheral blood mononuclear cells (PBMC) at effector to target cell ratios of 6.25 - 50. Percent lysis values will be normalized for percent NK cells within the PBMC preparations and are expressed as lytic units (LU) per 10^7 NK cells or LUNK as previously described (41, 71, 72). In addition intracellular IFNy will be assessed as described (42) (also see letter from [name]) in stimulated PBMCs. The number of IFNy+ NK cells will be assessed by flow cytometry gated on CD45+/CD3/ CD16+/CD56+ cells. Nonreactive isotype-matched mAb will be used as control.

Aim 1B. Determine whether an SSRI downregulates

inflammation in depressed HIV seropositive individuals. Hypothesis: SSRI is superior to placebo in decreasing biomarkers of inflammation (IL-6, CRP). Both MDD and HIV infection are associated with elevated levels of pro-inflammatory cytokines (for review see (7, 128-130). Although increased levels of many cytokines, inflammatory and oxidative stress markers were linked to either of those conditions extensive literature review show that IL-6 and CRP are two markers most consistently associated with both MDD and HIV infection. We

propose to use changes in those two markers as a primary outcome of our study. For example in our recent clinical trial with aprepitant, a compound with potential utility as a drug for depression and anti-inflammatory properties in HIV infected subjects, in non-depressed subjects we detected a decrease in plasma levels of IL-6 after 2 weeks of treatment within subjects ($p=0.02$) and between aprepitant and placebo ($p=0.02$) (131) (Figure 7). In addition to our primary variables (IL-6 and CRP) associated with inflammation, we will measure several other plasma markers of inflammation in HIV positive depressed subjects receiving SSRI or placebo (see C.4 Further Analyses).

Secondary Aim. Determine if improvement in depressive symptoms is associated with improvements in innate immunity and inflammation in HIV seropositive individuals.

Hypothesis: Reduced symptoms of depression after acute (10-week) treatment will correlate with increased

[figure not shown]

Figure 7. Changes in plasma levels of IL-6 in patients treated with aprepitant. IL-6 levels were measured in plasma of 48 patients HIV positive patients enrolled in aprepitant trial. 29 patients received medication (125, 250 or 375 mg per day), 19 received placebo for 14 days. Changes in IL-6 are shown as delta [IL-6] between baseline and after 2 weeks of treatment with aprepitant measured.

levels of innate immunity (LUNK and intra cellular IFNy in natural killer cells) and decreased levels of systemic inflammation (IL-6 and CRP).

C.3.2 Biostatistical Consideration and Analysis Plan

C.3.2.a Methods and Approach

Primary Aims: For Primary Aims 1A and 1B, participants will provide measures of innate immunity (LUNK and intracellular IFN- γ) and inflammation (IL6 and CRP) at baseline, and at weeks 2, 4, and 10. The measures will be continuously distributed, and we will use linear mixed effects models, probably after log transformation of a response, to estimate the effects of medication group and time on the distribution of the responses across the 10 week period. The explanatory variables in these models will be a binary indicator of medication group, variables representing time effects, together with possible group by time interaction terms. Time will be modeled as a discrete factor. For the covariance structure, we expect that a random intercept model will provide a good fit to the data, and will also compare other possible specifications using BIC comparisons.

Secondary Aim: In the Secondary Aim, we will examine relationships between the effects of Escitalopram versus Placebo on depressive symptoms and the effects on the primary biological responses. Hamilton scores will be obtained at baseline and at weeks 2, 4, and 10.

First, we will examine whether participants showing improvement in depression measures are also those showing improvement in primary biological measures. Here, we will calculate change from baseline scores for the Hamilton and for the four immunity measures. For each immunity measure and Hamilton, we will use bivariate mixed effects models to simultaneously model the pattern of depression change scores and immunity change scores across weeks 2 through 10. Here, for each of the four immunity measures, we are modeling the three Hamilton change scores and the three immunity change scores as a six-dimensional response, with explanatory variables of week, medication, and type of response (depression versus immunity). Our hypotheses, that decreases in Hamilton will be associated with increases in innate immunity, and with decreases in inflammation, will be tested by modeling the covariance structure, and testing individual covariances for significant differences from zero. We will perform these analyses separately for the four immunity responses.

Second, we will test whether Escitalopram has direct and indirect effects on the immune responses. The primary analyses (for Aims 1A and 1B) have addressed the total effect of Escitalopram on the four immunity measures. One set of analyses will use the confidence limit approach of MacKinnon et al (135, 136), to test whether changes in Hamilton score at week 2 (and, separately, at week 4) mediate the change in immunity measures at week 10. To obtain a complete picture of the possible mediation effects of depression, we will also perform these analyses using 50% reduction in HAM-D, and HAM-D ≤ 7 , as the measures of the direct effect of Escitalopram on depression. We will perform these analyses on the four innate immunity and inflammation responses separately. These mediation analyses focus on the end of treatment time point. To obtain information on longitudinal mediation across the full period, we will use latent growth curve mediation models (MacKinnon, 2008, 8.10-8.14). These models are similar to the bivariate mixed effects models described above, but here we include additional regression terms to isolate effects of depression on immunity across time, and random intercepts and slopes for the repeated depression scores and the repeated immunity scores, with the intercept and slope of the immunity response regressed on the intercept and slope of the depression response. MacKinnon (2008) describes how the estimated coefficients of these models can be used to provide estimates and confidence intervals for the indirect and direct effects of Escitalopram on immunity.

C.3.2.b Power Analysis and Sample Size Calculation for Primary Aims

We use two-sided hypothesis tests, and assume 10% loss to attrition over the 10 weeks. We set an overall alpha level of 5% within the innate immunity and inflammation hypotheses, so each Hypothesis is tested at alpha=0.025. We use the methods of Hedeker et al (122): assuming a within person correlation of 0.6 between visits, we have 80% power to detect a linear group by time effect (from week 0 through week 10) of Cohen's $d=0.40$ or higher, and 80% power to detect a main effect (from week 2 through week 10) of $d=0.4$ or higher.

C.3.3 Expected Outcomes, Potential Problems and Alternative Approaches

If successful, this trial will advance the field of HIV care by demonstrating the benefit of SSRI treatment on immune system homeostasis, marked by less innate immune suppression and less systemic inflammation, both of which are implicated in HIV pathogenesis. We expect to detect restoration of NK cell functions and decreases in levels of pro inflammatory markers as a result of SSRI treatment. Pro-inflammatory cytokines are thought to play a role in the pathophysiology of depression (4, 7, 86, 132). Although this is not an aim of the present study, data accumulated during our study will allow us to evaluate this relationship along with other patient characteristics (see C.4 Further Analyses). Both depression and HIV are associated with increased plasma levels of IFNy (133, 134) however based on previous observations (42) we expect to see decreased

IFNy production by stimulated NK cells from HIV+ subjects on cART. We will monitor if SSRI treatment or/and depression improvement will restore IFNy production. However if we do not detect changes in IFN- γ we will analyze other markers of NK activation and degranulation which are associated with both chronic HIV infection and depression (126) as noted below in C.4. Further Analyses.

We expect to see Immune changes prior to depression improvements suggesting direct SSRI effects on peripheral immune cells. Although unlikely, It is possible that a ceiling effect could be observed and both groups exhibit similar and maximal immune changes at a given time point. If that is the case the frequency of our measures will allow us to study the time course of these immune changes over time and over the time course of depression improvement which will further inform us about SSRI direct effects and depression improvement effects on immunity.

If successful, this rigorously designed clinical trial will advance the field of HIV care by demonstrating the immune benefits of SSRIs among depressed patients with well-controlled viral load – an increasingly prevalent population in the era of modern cART. Many large scale clinical trials encounter challenges with recruitment and retention. We will proactively monitor accrual and retention and should we encounter this challenge, we will initiate a response that will include consultation with the PMHARC Community Advisory Board to discuss recruitment barriers, additional avenues of recruitment and retention strategies. We will also maintain close communications with the Philadelphia Integrated Behavioral Health Initiative which has staff embedded within six of the largest HIV care sites in the city. These staff can help promote recruitment and facilitate retention should we need assistance.

C.4 Further Analyses

Innate Immunity, Inflammation and Virology: We will also assess the effects of SSRI on other important innate immune cell populations. These responses will be available at baseline and after 2, 4 and 10 weeks of treatment, so they will be analyzed using the approach described above for the primary outcomes of Aim 1. We will evaluate NK receptor expression before and after 10 weeks of SSRI treatment using Flow cytometry assay. Total NK cells will be characterized as CD45 $^{+}$ /CD3 $^{-}$ / CD16 $^{+}$ /CD56 $^{+}$. In addition, the expression of the following receptors will be assessed: NKp44, NKp46, NKp30 and CD107 using appropriate antibodies. CD56 bright and dim cells will be also assessed. CD56bright NK cells are associated with cytokine production while CD56 dim are linked to higher cytotoxic activity (137).

In addition to IL-6 and CRP we identified several other markers for further analyses based on the literature and our own immunologic investigations. Specifically, in the aripiprazole trial, in addition to IL-6 we also detected a decrease in plasma levels of TNF α and soluble CD163 (sCD163) and decreased expression of Programmed Death 1 (PD-1) receptor on CD4+ cells. PD-1 is known to suppress T cell activation (138). The assays will be done in conjunction with PMHARC Core E. sCD163 and TNF- α will be measured by standard ELISA techniques and PD-1 by flow cytometry. We will use a PD-1 panel established in our laboratory as a part of clinical trial U01 MH090325 (CD3/CD4/CD8/CD45RO/CD197/CD62L/CD95/PD-1/CD38/HLA-DR). We will also use the monocyte activation/polarization panel which we have developed (CD3/CD14/CD19/CD56/CD16/CD163/CD97/CD312/CD38/HLA-DR). Further we will quantitate expression of CD4, CCR5, and CXCR4 receptors on PBMCs and macrophages to evaluate SSRI effect we observed ex vivo (see C1.9.c). We will measure both fluid phase (plasma) and cellular markers of innate immunity and inflammation using multiplex and flow cytometry technology. These measures will be performed on stored plasma samples and cryopreserved PBMCs.

We expect to find undetectable levels of virus in plasma (<40 copies/ml) in most subjects because all subjects will be on a stable cART regimen. Therefore, data on plasma viral load will be used primarily for monitoring cART adherence. In contrast, we expect to find low but detectable levels of viral DNA in most subjects. Restoration of NK functions may lead to decreased viral DNA levels. We will analyze if such a decrease is linked to SSRI treatment or improvement of depression in general. We will also establish a repository of plasma and frozen PBMC samples from the 180 depressed HIV+ subjects. This repository will allow us to evaluate other markers associated with depression and/or chronic HIV infection such as oxidative stress (e.g. malondialdehyde), markers of monocyte activation (e.g. neopterin) and any other newly identified molecules during the period of the current study. We will evaluate monocyte activation/polarization profile since we expect that changes in plasma cytokines may affect monocyte polarization which in turn may influence both depression and HIV infection (30-33).

Effects of patient characteristics: Differences in patient demographics (such as age and gender) and characteristics (such as depression severity, levels of life stress, social support, neurocognitive capacity, time since HIV diagnosis, endocrine status, and systemic inflammation level) could potentially moderate the effects of SSRI treatment on our primary outcomes. Some research has suggested that baseline levels of CRP (139), IL-6 and TNF- α (7, 86, 140, 141) and of other biological indicators (7, 86, 132) may influence the effects of

SSRI on depression. We will perform a series of moderator analyses (142) to address these questions. The potential moderators will be included as main effects and as interactions with group in the analyses described above for the primary responses. We will use multivariate analyses analogous to the univariate analyses to examine SSRI effects on a wider range of biological responses to include endocrine hormones (cortisol, ACTH, DHEA), as well as the flow cytometry panels noted above.

C.5 Missing Data and Nonadherence For the primary analyses described above, premature discontinuation from treatment and occasional missing weekly appointments will lead to incomplete data. The mixed effects models for Aim 1, Hypothesis 1 described above can make use of all available data provided by subjects, but the inferences drawn from them will be unaffected by the missing data only if the missing data can be regarded as ignorable. For the other primary responses, dropouts will not provide any responses, so the basic models require ignorable dropout. To assess the sensitivity of our analyses to this assumption, we will also use selection models (143) to examine the effects of missing data: we will explicitly model the probability of premature discontinuation at a time point as a function of baseline characteristics and responses at previous time points, using a logistic regression model. For the longitudinal analyses of Aim 1, Hypothesis 1, these probabilities will provide time varying (inverse) weights for reruns of the primary analysis. For the other primary hypotheses, the overall probability of dropout will be used as a weight, and incorporated into a weighted analysis of these hypotheses. We will perform these analyses in a range of assumptions on the dropout process and assess the sensitivity of results to them. To account for possible non-adherence to assigned intervention, we will use self-report of pill ingestion and MEMS caps, as well as RNA viral load for cART. We will use the methods of Nagelkerke et al (144, 145), to obtain estimates of the intervention effect in a population compliant with treatment i.e. the Complier Average Causal Effect (CACE).

